115 injection, but not for use in pumps. In Europe it was approved for use by injections and in
116 insulin infusion pumps. In both the US and Europe it was approved for use in pregnancy.
117 There has been one study published on pump compatibility of Fiasp® ⁵ which showed a
118 premature end of infusion set wear in 10% of 210 Fiasp® infusions, and 4% of 98 aspart
119 infusions (p=ns).

120

121 1.2.2 Medtronic 670G Hybrid Closed-loop

122 The Medtronic 670G hybrid closed loop system is the first fully integrated system designed
123 for continuous day and night closed-loop control. The system requires meal announcement
124 with an estimate of carbohydrate intake and a premeal insulin bolus to optimize glucose
125 excursions. We published the first results of using this system in 2015 in adolescents
126 attending a diabetes camp ⁶, and the 670G system was approved for commercial sale by
127 the FDA on September 28th, 2016. We have had adolescents using this system for 2 ½
128 years, 7-14 year olds using the system for 15 months, and 5 to 6 year olds have been using

129 this system at Stanford for over 3 months as part of the pivotal trials with extended use of
 130 the system after the initial 3 month pivotal phase. Both the adult and pediatric clinics now
 131 have patients using the 670G system.

132

133 **Figure 1-3:** Medtronic 670G system: Medtronic 670G pump, Guardian 3 continuous
 134 glucose sensor, and Bayer Link glucose meter.

135

136

137 The safety and effectiveness of the in-home use of a hybrid closed-loop (HCL) system was
 138 investigated in adolescents (n = 30, ages 14–21 years) and adults (n = 94, ages 22–75
 139 years) with type 1 diabetes in a multicenter pivotal trial ⁷. The 670G system was used
 140 during a 2-week run-in phase without HCL control, or Auto Mode, enabled (Manual Mode)
 141 and then in Auto Mode during a 3-month study phase. Data from the trial is seen below, in
 142 Table 1.

143 **Table 1:** Comparison of glucose control and insulin doses from the 2 week baseline
 144 data compared to the 3 months of 670G hybrid closed loop use ⁸

[figure not shown]
	Run In (Baseline)	3 month Data	p
HbA1c	7.4 ± 0.9	6.9 ± 0.6	<0.001
% <70 mg/dL	6.4 ± 5.3	3.3 ± 2.0	<0.001
% 71-180 mg/dL	66.7 ± 12.2	72.2 ± 8.8	< 0.001
% >180 mg/dL	27.4±13.7	24.5±9.2	< 0.001
Mean Glucose	150.2±22.7	150.8±13.7	NS
Within Day CV	33.5±4.3	30.8±3.3	< 0.001
TDI	47 ± 22	51 ± 27	< 0.001

145

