- 286 4) Assess if Fiasp® becomes less effective over the life an infusion set (are sets
287 changed more frequently)
- 288 5) Assess how the 670G performs when Fiasp® is used:
 - 289 a. Do insulin-to-carbohydrate ratios need to be modified
 - 290 b. Does duration of insulin action need to be modified
 - 291 c. Is more or less basal insulin delivered
 - 292 d. Does the total daily dose change
 - 293 e. Does the performance of the 670G change overnight (MN to 6AM)
294 and during the day (6AM to MN) in terms of time in range, mean
295 glucose and % of readings <70 mg/dL.

296

297 will include both males and females and an enrollment goal will be to achieve an

298 approximately equal sex distribution. Their total daily insulin dose should be at least
299 0.3 units/kg/day and they should be eating at least 60 grams of carbohydrate each
300 day.

301

302 **General Considerations**

303 The study is being conducted in compliance with the policies described in the study
304 policies document, with the ethical principles that have their origin in the Declaration
305 of Helsinki, with the protocol described herein, and with the standards of Good
306 Clinical Practice.

307

308 **CHAPTER 2: SUBJECT ENROLLMENT AND STUDY INITIATION**

309

310 **Study Enrollment and Duration**

311 Part 1: Randomized cross-over, blinded study with assessment of meal
312 pharmacodynamics: up to 20 subjects will be studied and the studies for each
313 subject will last 6 weeks.

314 Part 2: Long term use of Fiasp®. We will recruit up to 20 subjects who are using
315 Fiasp® insulin, they are not excluded if they were in Part 1, in fact subjects in part 1
316 will be encouraged to continue into part 2 of the study. Duration is up to 6 weeks, or
317 until subject decides to stop using Fiasp®.

318

319 **Eligibility and Exclusion Criteria**

320

321 **Eligibility Criteria**

322 To be eligible for the study, a subject must meet the following criteria:

- 323 1. Clinical diagnosis of type 1 diabetes and using 670G pump for at least 1
324 month, and willing to have the 670G pump downloaded into a Carelink
325 Clinical research database.
- 326 2. The diagnosis of type 1 diabetes is based on the investigator's judgment; C-
327 peptide level and antibody determinations are not needed.
- 328 3. Age ≥18 years
- 329 4. Using Novolog or Fiasp® insulin at time of enrollment
- 330 5. Willing to use Fiasp® insulin
- 331 6. Total daily insulin dose is at least 0.3 units/kg/day

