529 670G pump to a research Carelink account every 2 weeks. Their data will be
530 reviewed within 3 days by the clinicians managing the study at each research
531 clinical site. An email, text or phone call will be made to the subject after reviewing
532 their pump/sensor data. Recommendations for dosage changes will be recorded on
533 a case report form or directly into RedCap. The study investigators will meet every
534 2 to 4 weeks during the study to review clinical issues and insights that have been
535 observed.

536

537 To assess the long term effect of using Fiasp® on infusion sites and insulin action,
538 they will be asked to use Fiasp® as long as they see benefit in using it after the
539 initial meal boluses testing is completed. Each time they change their infusion set,
540 we will ask them to examine the site for any bleeding, redness or induration, and
541 measure these changes and take a picture if there are any findings. (See
542 Documentation of infusion site reactions). We will have them download to a
543 CareLink research data base every two weeks to look at their total daily insulin
544 requirements, glucose values, and basal insulin requirements with extended use of
545 Fiasp®. They will have an email sent to them every 2 weeks by RedCap to assess
546 for issues they have observed while using Fiasp®.

547

548 *Documentation of infusion site reactions:* At home subjects will exam their infusion
549 set site when they are changing an infusion set and assess for bleeding, signs of a
550 local tissue reaction or infection. They will record redness, induration, and bruising
551 in mm, and call one of the investigators if there is more than 10 mm of erythema or
552 induration. They will be given a ruler for making these measurements. If there is
553 more than 3 mm of induration or redness they will be asked to take a picture and
554 enter these measurements and send a text to the study coordinator or submit the
555 information directly into RedCap.

556

557 They will be instructed to replace the infusion set if:

- 558 1. Their ketone level is greater than 0.6 mmol/L,
- 559 2. There is evidence of infection at the infusion site
- 560 3. Their blood glucose (meter) does not decrease by at least 50 mg/dL within 1
561 hour of a correction bolus for unexplained hyperglycemia with a blood
562 glucose greater than 250 mg/dL.
- 563 4. There is a pump occlusion alarm.

564

565 **CHAPTER 4: ADVERSE EVENT REPORTING AND PROTOCOL MONITORING**

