772 the time of the bolus. The glucose at the time of the breakfast bolus (Time 0) will be
773 set to 0 mg/dL for each meal, and the remaining CGM values were adjusted
774 proportionally to allow analysis of postprandial glucodynamic parameters. We will
775 utilize a mixed-effects model accounting for crossover study design of the study with
776 the sequence of treatment nested within the patient. Breakfast meals are excluded
777 from postprandial analysis if: 1) the rate of change was greater than 0.3mg/dL/min
778 in the 1 hour prior to breakfast, 2) subjects gave a subsequent bolus prior to 120
779 minutes following the breakfast bolus, or 3) subjects deviated from their typical
780 breakfast. Dinner meals will be assessed when there has been no additional food
781 intake after dinner. The duration of insulin delivery to cover the meal will be
782 determined by the time it takes the post prandial glucose to reach 160 mg/dL
783 beyond 1 hour of eating. The peak glucose will also be recorded.

783

784 During the 6 week optimization study (Part II) we will use data obtained during the
785 first two weeks of the study (before data was reviewed and changes made by the
786 investigators) to data obtained during the last two weeks of the 3 month optimization
787 period. We will compare the following measurements using paired t-tests for data
788 with a normal distribution and a Mann-Whitney rank sum test for data that is not
789 normally distributed:

790

a) time in range (70-180 mg/dl)

791

b) percent time <70 mg/dl,

792

c) mean glucose,

- 793 d) glucose CV,
- 794 e) total daily insulin dose,
- 795 f) total daily basal insulin,
- 796 g) insulin delivery form MN to 6AM, and 6AM to MN
- 797 h) CHO:I ratios at breakfast, lunch and dinner
- 798 i) Active insulin time
- 799 j) Number of days between infusion set changes
- 800 k) Erythema (mm) and induration (mm) at infusion sites when they are changed
- 801 l) Average daily insulin, and mean glucose for each day of infusion set wear
- 802 m) Number of episodes of unexplained hyperglycemia in the first month vrs the
- 803 last month
- 804
- 805
- 806
- 807

808 **CHAPTER 7: REFERENCES**

809

- 810 1. Heise T, Hovellmann U, Nosek L, Sassenfeld B, Thomsen KMD, Haahr H.
811 Pharmacokinetic Properties of Fast-acting Insulin Aspart Administered in Different
812 Subcutaneous Injection Regions: Response to the commentary by Nuggehally R. Srinivas.
813 Clinical drug investigation 2017.

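### Part 2's wear-day averages tend to understate loss of insulin effect as a set ages, because failing sets are replaced and no reason for a change is planned to be recorded

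*Combined protocol and SAP*

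**What the plan says.** - **The aim.** Section 1.4, Part II goal 4: "Assess if Fiasp® becomes less effective over the life an infusion set (are sets". The parenthesis goes on to name more frequent changes as the sign to look for.
- **The measures.** Among the Part II items in Chapter 6, item j is "Number of days between infusion set changes", item l is "Average daily insulin, and mean glucose for each day of infusion set wear", and item m begins "Number of episodes of unexplained hyperglycemia in the first month vrs the" and ends with the last month.
- **The contrast.** All items sit under one comparison: the first two weeks against the last two, by paired t-test or rank sum test, with every subject on Fiasp throughout.
- **The replacement rule.** Chapter 3, Part 2: "They will be instructed to replace the infusion set if" any of four criteria is met. These are ketones above 0.6 mmol/L, site infection, an occlusion alarm, and a failed correction of unexplained glucose above 250 mg/dL. The last is worded "Their blood glucose (meter) does not decrease by at least 50 mg/dL within 1" hour of the bolus.
- **What is recorded at a change.** In Part 2, subjects inspect the "set site when they are changing an infusion set and assess for bleeding, signs of a" local reaction or infection, and they measure what they find. Why the set was changed is not listed. Chapter 6 neither uses the replacement criteria as an outcome nor says how sets already removed enter the wear-day averages.

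**The concern.** Two of the four criteria, raised ketones and a failed correction, can themselves signal that insulin from that set is no longer working. A set that meets one is taken out, and the hours that follow belong to day 1 of its successor. The later wear days are thus selected, in part, on the outcome goal 4 is about. This is informative removal, and enrolling more subjects would not cure it.

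Item j might be expected to compensate, since early replacement shortens the interval. But it averages those replacements with routine changes, which may shift for unrelated reasons. Item m keeps counting episodes after a set is gone, but it is tied neither to a set nor to a wear day. The risk is that Part 2 reports little change over set life when a minority of sets did fail early.

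**Working it through.** Part 2 has no sample size calculation, power or expected effect, so there is no design figure to reproduce. The one related figure is the background result in section 1.2.1, "premature end of infusion set wear in 10% of 210 Fiasp® infusions, and 4% of 98 aspart" infusions, reported as not significant. Taking 21 of 210 and 4 of 98, Fisher's exact test gives p = 0.11, which agrees.

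**Inputs from the documents:** early-end rates of 4% and 10% (1.2.1, used only as illustrations); up to 20 subjects (Chapter 2); two-week windows (Chapter 6).

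**Assumed inputs:** routine wear 3 days; early-ended sets last 1.5 days; sets removed before day 3 would have averaged 60 to 100 mg/dL above those remaining.

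**Step 1. Item l, day-3 mean.** If a share p of sets is gone and would have run d above the rest, the mean over all sets is the observed mean plus p × d. The understatement is therefore p × d.

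| p | d = 60 | d = 100 |
|---|---|---|
| 0.04 | 2.4 mg/dL | 4 mg/dL |
| 0.10 | 6 mg/dL | 10 mg/dL |

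**Step 2. Allowing for delayed replacement.** Assume 4-day wear and 20% of sets degrading, with onset equally likely on day 2, 3 or 4 and glucose rising 60 mg/dL per day from onset. The true day-1-to-day-4 rise is 0.20 × (180 + 120 + 60)/3 = 24.0 mg/dL. The observed rise depends on the daily chance that a degraded set is replaced and on how much of the failing day is counted:

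| Daily replacement | None counted | Half | All |
|---|---|---|---|
| 50% | 6.4 | 9.3 | 12.0 |
| 80% | 1.5 | 4.3 | 6.9 |
| 100% | 0.0 | 2.4 | 4.6 |

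Over wear of 3, 4 and 6 days and 10% to 30% of sets degrading, the observed rise was always below the true one. It ranged from 0% of it to about 72% (19.5 of 27.0 mg/dL: 3-day wear, 30% degrading, 50% replacement, failing day fully counted).

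**Step 3. Item j.** Mean interval = (1 − p) × routine wear + p × 1.5.
- p = 0.04: 0.96 × 3 + 0.04 × 1.5 = 2.94 days.
- p = 0.10: 0.90 × 3 + 0.10 × 1.5 = 2.85 days.
- p = 0.10 with routine wear at 3.1 days: 0.90 × 3.1 + 0.15 = 2.94 days.

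A 2.5-fold rise in failures moves the mean by 0.09 day, and a 0.1-day lengthening of routine wear cancels it. With 20 subjects and an assumed SD of change of 0.3 to 0.5 day, a paired t-test has about 25% to 12% power for 0.09 day.

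**Step 4. What separate counting can deliver.** At 3-day wear, 20 × 14/3 gives about 93 sets per two-week window, so about nine early-ended sets at 10%. Treating sets as independent, power is about 36% for 4% against 10%, and 48% for 10% against 20%.

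**The case against.** - **Not every failing set leaves.** A reader might infer that later wear days hold only working sets, so that any real loss would look like none. The documents do not support this. The glucose criterion needs both a value above 250 mg/dL and a failed correction, so gradual loss below that level stays in the averages. The 670G adjusts basal delivery (section 1.3), so partial loss could appear as more insulin, which is half of item l. No text drops the hours before a replacement. In Step 2, complete masking arises only when every degraded set is removed at once and its failing day goes uncounted.
- **The planned contrast is a different one.** A reader might also take 6 to 10 mg/dL as the bias in the Chapter 6 comparison. It is not. That comparison sets early weeks against late weeks, all on Fiasp, and if removal is similar in both windows its effect largely cancels. This stands, but it does not rescue goal 4: a contrast between calendar windows does not itself test change within a set.
- **Other data exist.** Item m is a further, indirect signal, although its first and last months overlap if Part 2 lasts 6 weeks. (Chapter 6 also refers to 3 months; the two must be reconciled.) Pump, sensor, glucose and ketone meter data are downloaded (Chapter 4, Other Risks), so several criteria may be recoverable. What is missing is a planned classification rather than all of the underlying data.
- **Item j is the sponsor's own indicator, in an unpowered pilot.** Both are true, so item j should be kept. But low power concerns precision, whereas this is a matter of direction. The 4% and 10% compare aspart with Fiasp, a contrast Part 2 does not make, so they serve only as illustrations.

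**Conclusion.** The concern holds in a limited form. For goal 4, a day-1-to-later-day reading of item l tends to understate loss of effect, because sets meeting a replacement criterion leave the later days. Item j registers those sets but dilutes them with routine changes, and item m cannot be placed by set or wear day. The direction held in every scenario tried. The size cannot be had from the documents: 6 to 10 mg/dL rests on the assumed 10% removal and 60 to 100 mg/dL difference, and the 0.09-day movement in item j rests on the assumed wear times. The documents do not show that a loss would be hidden altogether. The point merits a change because it limits what Part 2 can say on one of its stated goals, and the reason for a change may be hard to establish afterwards.

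**What to change.** 1. **Site record (Chapter 3, Part 2).** At each set change, add one field: routine, or which of the four existing replacement criteria was met. Check it against the downloaded pump, sensor and meter data.
2. **Item j.** Keep it, and report it separately for routine and early changes.
3. **New descriptive measure.** Report the share of sets ended early by a criterion, by wear day.
4. **Item l.** Compare each set with its own day 1. State that the hours before an early replacement stay with the set that failed, and show early-ended sets separately. The within-set comparison alone is not enough, since a removed set still has no later days; the separate display and the share in item 3 cover that gap.

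The replacement criteria themselves are unchanged.

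The cost is one tick-box on a record subjects already make, and a few lines in Chapter 6. The downsides are slight extra burden, reasons that are partly self-reported, and low precision: with roughly nine early-ended sets per window at a 10% rate, the breakdown by wear day can only be descriptive.

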416 answered about the details regarding authorization.

417

418 **CHAPTER 3: PROTOCOL PROCEDURES**

419

420

421 **Visit 1:** Informed consent process:

422 *Informed consent process:* The protocol will be reviewed with the subjects, they will
423 be given time to read the informed consent and ask any questions about the study.

424

425 *History and physical exam:* Including age at diagnosis of diabetes, duration of
426 diabetes, any retinal, renal or cardiac conditions. Height, weight, and examination
427 of skin where infusion sets are inserted.

428

429 *Laboratory tests:* Point of care A1c will be obtained and urine pregnancy test will be
430 obtained on all women who are pre-menopausal.

431

432 **Training on home procedures:**

433

434 Blood glucose monitoring: Subjects will test blood glucose using a Bayer Contour
435 Next Link home glucose meter at least 3 times daily. Subjects will be instructed to
436 check blood ketones using a blood ketone meter if there is unexplained sensor
437 hyperglycemia and the blood glucose meter reading is greater than 250 mg/dL.

438

439 Calibration of Guardian Sensor: They will be instructed to calibrate the Guardian
440 sensor before breakfast and before dinner each day when there are no rate of
441 change arrows and after washing their hands or using the second drop of blood.
442 They will also be instructed to calibrate if the Guardian is showing more than a 20%
443 error when compared to their Contour Next blood glucose reading and the Guardian
444 is not showing a rapid rate of change.

445

446 Replacement of Guardian Sensor: If the Guardian sensor stops functioning during
447 the study, the subjects will insert a new sensor.

448

449 **Determination of an infusion set failure:**

450 They will be instructed to replace the infusion set if:

451

1. Their ketone level is greater than 0.6 mmol/L,

452

2. There is evidence of infection at the infusion site

453

3. Their blood glucose (meter) does not decrease by at least 50 mg/dL within 1
454 hour of a correction bolus for unexplained hyperglycemia with a blood
455 glucose greater than 250 mg/dL.

455

4. There is a pump occlusion alarm.

456

457

458 *Documentation of infusion site reactions:* At home they will exam the infusion set
459 site at time of infusion set failure for signs of infection. They will record bleeding,
460 redness, induration, and bruising in mm, and call one of the investigators if there is

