461 more than 10 mm of erythema or induration. They will be given a ruler for making
462 these measurements. If there is more than 3 mm of induration or redness they will
463 be asked to take a picture and enter these measurements into a text to the study

464 coordinator or submit the information directly into RedCap.

465

466 The goal will be to have sensor wear at least 80% of the time and in automode at
467 least 70% of the time. The pump will be uploaded to a research Carelink account
468 each week. While in the blinded phase of the study the clinical staff will refrain from
469 making changes to 670G pump settings unless requested by the subject or for
470 safety reasons such as an episode of severe hypoglycemia (unconsciousness or
471 seizure), >10% time <70 mg/dl, or >20% of the time over 250 mg/dl.

472

473 **Part 1: Randomized, cross-over, blinded study to assess any adaptations of**
474 **the 670G pump to Fiasp® and to assess meal pharmacodynamics of Fiasp®**
475 **compared to aspart with a typical breakfast in the home environment**

476

477 Participants will have a 2 week run-in on their usual home insulin (aspart of Fiasp®).
478 During the run-in, their pump will be downloaded weekly, reviewed by the clinical
479 staff and adjustments will be made to their settings as needed to optimize their
480 glycemic control. Participants will then be randomly assigned to 2 sequences of
481 testing starting with either aspart or Fiasp®. They will use each insulin for two
482 weeks. The participants and the investigators will be blinded to the insulin. During
483 the second week of using a blinded insulin they will have the meal
484 pharmacodynamics testing. They will then cross-over to the other insulin and
485 during the second week they will repeat meal pharmacodynamics testing. At the
486 end of each week they will upload their 670G pump to a Carelink clinical (research)
487 account and it will be reviewed by the research staff for safety purposes.

488

489 Procedure for meal testing. For each week of meal testing they will be asked to
490 have 3 days with a consistent breakfast that is the same for all 6 days they are
491 doing a meal test (3 days on each insulin). The breakfast studies should ideally
492 occur on standard work days (not holidays or weekends). On these three days they
493 will be asked to have a dinner with at least 30 grams of fat and no additional food in

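### Part II item m compares raw counts of unexplained hyperglycemia between two months, with no denominator for the time in which an episode could be observed

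*Combined protocol and SAP*

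**What the plan says.** Chapter 6 (Statistical Considerations) lists 13 Part II comparisons, a to m. Item m reads "Number of episodes of unexplained hyperglycemia in the first month vrs the" last month. The tests for the whole list are named just above it: "period. We will compare the following measurements using paired t-tests for data" that are normally distributed, and a Mann-Whitney rank sum test otherwise. No rate, offset, minimum wear or episode definition is given.

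The length of Part II is stated in two ways within one sentence. It opens "During the 6 week optimization study (Part II) we will use data obtained during the" first two weeks, and goes on to compare them with the last two weeks of a 3-month period. Chapter 2 (Study Enrollment and Duration) allows up to 6 weeks, or less if the subject stops Fiasp, while its HbA1c section refers to a 3-month observational study. Chapter 5 uses data up to the time of withdrawal.

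Three places in Chapter 3 bear on how an episode might be seen:

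- Sensor wear: "The goal will be to have sensor wear at least 80% of the time and in automode at" least 70%. No analysis rule depends on this goal.
- Ketone checks: subjects are to "check blood ketones using a blood ketone meter if there is unexplained sensor" "hyperglycemia and the blood glucose meter reading is greater than 250 mg/dL". Meter testing is required at least 3 times a day, whether or not a sensor is worn.
- Set replacement after a correction bolus for unexplained hyperglycemia, repeated in the Part 2 section, is judged on the meter: "Their blood glucose (meter) does not decrease by at least 50 mg/dL within 1" hour.

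**The concern.** A count reflects both the event rate and the time under observation. The CGM measures in the same list (percent time, mean glucose, CV) are averages or proportions of the readings available, so lost time does not shrink them mechanically. Item m has no such protection. If the last window holds less observed time than the first, the expected count falls with no change in the rate, and a real increase can be masked.

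The error would run towards reassurance. Part II asks whether Fiasp becomes less effective over the life of an infusion set, and unexplained hyperglycemia is one of the measures that bears on this. Fewer episodes in the last month could be read as set problems settling when subjects were simply observed for less time.

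**Working it through.** The plan gives no episode rate, power or sample-size figure, so there is nothing to reproduce. The true rate is held constant below. Wear fractions, off-sensor detection, episode rates and the length of a month are assumptions.

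**1. Early stopping.** Take 42 days (6 weeks) and a 28-day month. The windows are days 1–28 and days 15–42. A subject who stops at day 28 contributes 28 days to the first window and 28 − 14 = 14 days to the last, so the expected count ratio is 14/28 = 0.50. If the last month is instead counted back from the subject's own last day, both windows are days 1–28 and the difference is zero by construction. The plan does not say which applies.

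**2. Sensor wear.** Let w1 and w2 be wear in the first and last windows, and d the detection off-sensor relative to on-sensor (0 = sensor only, 1 = the meter finds all). Then

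ratio = [w2 + (1 − w2)d] / [w1 + (1 − w1)d]

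| Wear, first to last | d = 0 | d = 0.5 | d = 1 |
|---|---|---|---|
| 80% to 80% | 1.00 | 1.00 | 1.00 |
| 90% to 80% | 0.80/0.90 = 0.89 | 0.90/0.95 = 0.95 | 1.00 |
| 90% to 70% | 0.70/0.90 = 0.78 | 0.85/0.95 = 0.89 | 1.00 |

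**3. Effect on the test.** Simulation used 20 subjects, separate windows, gamma-Poisson counts averaging 2 to 8 true episodes a month, and a two-sided paired t-test at 0.05. The chance of a falsely significant fall (nominal 2.5%) was:

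- wear 90% to 80%: 6% to 14% at d = 0, and 4% to 6% at d = 0.5;
- wear 90% to 70%: 15% to 45% at d = 0, and 6% to 14% at d = 0.5;
- equal wear of 80%: about 2.5% throughout.

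**4. Overlap of the windows.** Overlap = max(0, 2 × month − study length). In 42 days this is 2 × 28 − 42 = 14 days (50% of each window), or 2 × 30 − 42 = 18 days (60%). In 84 to 91 days there is none. Overlap dilutes any difference, real or spurious. With wear of 90%, 80% and 70% in successive fortnights and d = 0, the ratio is (0.80 + 0.70)/(0.90 + 0.80) = 0.88, against 0.70/0.90 = 0.78 for separate windows.

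**5. Choice of denominator.** Dividing all episodes by sensor-worn time multiplies the ratio by w1/w2. At d = 0.5 this over-corrects: (0.90/0.95) × (0.90/0.80) = 1.07 for 90% to 80%, and (0.85/0.95) × (0.90/0.70) = 1.15 for 90% to 70%. If only episodes that start during wear are counted, the expected count is rate × worn time. The ratio per worn hour is then 1.00 whatever the meter finds.

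**The case against.** The strongest reply is that nothing ties item m to the sensor. The ketone instruction is not an episode definition, and it also needs a meter reading above 250 mg/dL. The set-replacement rule, which is the one unexplained-hyperglycemia rule repeated for Part 2, names only the meter. Meter tests continue without a sensor. If item m follows that rule, dependence on wear could be small or nil. Equal wear also leaves the comparison unbiased, and no passage gives a reason to expect a fall. The 80% goal stands beside text on weekly uploads and the blinded phase, so it is unclear whether it covers Part II at all. Item m is one of 13 exploratory comparisons in a pilot described as unpowered, and set-change interval, site reactions and performance by day of set wear are covered by items j, k and l.

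All of this stands, and it limits the size of the point. It does not supply a denominator: early stopping shortens observation under either detection route.

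A reader might infer more: that episodes are mainly sensor-detected, that the monthly count is therefore up to 20% low at the wear goal, and that a fall in wear will appear as improvement. The documents do not support this. The detection source is undefined. A 20% shortfall common to both windows cancels in the comparison. The 88% median for adults in Section 1.2.2 is system use in another trial, not sensor wear in this one.

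**Conclusion.** Item m should not be left as a raw count. It has no exposure term, and observed time can differ between windows through early stopping, withdrawal or a change in wear. The direction and size of any bias in this trial cannot be known from the documents. For an assumed fall in wear from 90% to 80%, the spurious ratio lies between 0.89 (sensor-only detection) and 1.00 (full meter detection), with 0.95 halfway. It is 1.00 whenever wear is equal. Those figures assume complete, separate windows and a constant true rate.

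The overlap of 14 to 18 days is firmer, since it follows from the stated 6 weeks and any ordinary meaning of a month. It disappears only under the 3-month reading, so the two statements must be reconciled. Severity is minor: the pilot's main comparisons are untouched, and the correction is nearly free.

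**What to change.** In Chapter 6:

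- Define an unexplained hyperglycemia episode and state whether its data source is the sensor, the meter or both.
- Replace the count with a rate per observed time in each window, for example a Poisson or negative binomial model with log observed time as offset and subject as random effect.
- Use sensor-worn hours as the denominator only for episodes that start during sensor wear. Report meter-only episodes beside it, per day of follow-up.
- Show sensor wear and days of follow-up by window.
- Reconcile the 6-week and 3-month statements, then fix two windows that do not overlap and say how subjects who stop early are placed in them. The first and last two weeks, already used for the Part II list, are separate even in 6 weeks (14 + 14 = 28 of 42 days).

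The cost is wording and slightly more analysis. The pump, sensor and meter downloads are already collected. The downside is two episode summaries instead of one. An offset also does not correct for subjects who leave because of infusion-set trouble, so reasons for stopping should be listed alongside.
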